6.6 Investigational Product Accountability and Compliance

6.6.1 Dispensing Investigational Product

During the confinement period from Day -3 to Discharge at Day 6, CC, and from Day 1 onwards to Discharge at Day 6, CHTP 1.2, will be dispensed to the subjects stick by stick. One will be allowed at a time and documented in an appropriate log.

On each day of the confinement period, the time of dispense and return for each product (CC/CHTP 1.2) use has to be documented from Day -3 until Discharge at Day 6.

During the ambulatory period, subjects in the CHTP 1.2 arm will be provided with CHTP 1.2. Up to two extra deliveries of CHTP 1.2 in between two visits, e.g., between Visit 2 and Visit 3, will be carried out. Subjects in the CC arm will buy their CCs and will not be reimbursed.

Subjects will have free access to their assigned product (CC or CHTP 1.2) during Visit 2, Visit 3 and the first day of Visit 4 of the ambulatory period.

On the second day of Visit 4 (Day 91), subjects who wish to smoke CC or use other nicotine/tobacco-containing products will be allowed to do so, but only after the end of 24-

Confidentiality Statement

Data and information contained in this document are considered to constitute trade secrets and confidential commercial information, and the legal protections provided to such trade secrets and confidential information are hereby claimed under the provisions of applicable law. No part of this document may be publicly disclosed without the written consent of Philip Morris Products S.A.

hour urine collection and after spirometry and sampling for CYP2A6 activity have been performed.

CHTP 1.2 will not be promoted for commercial distribution or test market.

6.6.2 Storage and Accountability

CHTP 1.2 and CC will be stored in a secured storage site with access limited to authorized personnel only. The study collaborator designated by the PI will be responsible for the storage and accountability of the IPs in accordance to Sponsor's requirements. CHTP 1.2 must be stored under controlled conditions (temperature and humidity), whereas CCs can be stored in normal conditions (at ambient temperature with no temperature or humidity control).

During the confinement period subjects will return each used CHTP 1.2 or butt of each used CC immediately after use to the site collaborators for accountability. The time of return of the products will be documented in an appropriate log.

During the ambulatory period subjects will record daily product use in the product use diary and return any unused packs, empty packs and partially used packs of CHTP 1.2 to the site for accountability after check-in at the investigational site at Visit 2, Visit 3 and Visit 4.

On the first day of Visit 4, after the collection and check of empty/partially used CHTP 1.2 packs for accountability, partially used packs will be returned and/or new packs will be handed out to the subjects, if requested, for use until 11:00 PM at the latest. All packs must be returned to study staff at the end of the first day of Visit 4.

No IP accountability will be done for CC in the CC arm during the ambulatory period.

Unused CCs given to the site collaborators at Admission will be given back to the subjects at Discharge on Day 6.

6.6.3 Investigational Product Retention

Used and unused CHTP 1.2 will be destroyed or returned to the Sponsor upon study completion as per instructions which will be provided by the Sponsor in due time.

6.6.4 Adherence to Investigational Products

During the confinement period, adherence to product allocation for both study arms will be ensured by strict distribution of the products (stick by stick) and collection of the CC butts and CHTP 1.2 after each use. Distribution and return of these products will be documented in appropriate logs.

Confidentiality Statement

Data and information contained in this document are considered to constitute trade secrets and confidential commercial information, and the legal protections provided to such trade secrets and confidential information are hereby claimed under the provisions of applicable law. No part of this document may be publicly disclosed without the written consent of Philip Morris Products S.A.

During the ambulatory period, from Discharge on Day 6 until Discharge at Visit 4, subjects in both study arms will capture the number of the product used (e.g., menthol and non-menthol CC, CHTP 1.2, or any other tobacco /nicotine-containing products including nicotine replacement therapy [NRT]) in the product use diary on a daily basis. The product use diary will be supplied by Sponsor and distributed to the subjects by the study site collaborators. The data captured in the product use diary will serve as the method to assess adherence in both arms. On Day 6, the adherence to the assigned product will be ensured using both the accountability log (from 06:30 AM until Discharge) and the product use diary (in the subjects daily report of product use). In case of discrepancy between the log and the diary entries, the diary will be considered as the primary source data.

6.7 Restrictions

6.7.1 Smoking Restrictions

6.7.1.1 Screening Visit and Confinement Period

At the Screening Visit pre- and post-bronchodilator spirometry will be done at least 1 hour after having stopped smoking. At the end of the Screening Visit, subjects will be instructed not to smoke in the morning prior to Admission on Day-3. On the Admission Day, smoking will be allowed only after the blood drawing for CYP2A6 activity has been taken, on Day -2, only after the Cough Questionnaire has been completed, and on the Day of Discharge (Day 6) only after twenty four-hour urine collection of Day 5 and the Cough Questionnaire have been completed, and the blood drawing for CYP2A6 activity assessment has been performed.

During the confinement period, smoking will generally only be allowed during the designated smoking times, from 06:30 AM to 11:00 PM.

Subjects will not have free access to their CC or CHTP 1.2 which will be dispensed by the site collaborators individually as described in section 6.6.1.

To avoid cross smoke contamination between the two study arms, subjects must use their assigned product (CHTP 1.2 or CC) in separate smoking rooms.

Using CHTP 1.2 or smoking CC will not be allowed during study procedures.

6.7.1.2 Ambulatory Period

Subjects in the CHTP 1.2 arm will be instructed to exclusively use CHTP 1.2.

On the first day of Visit 2, Visit 3, and Visit 4, subjects in the CHTP 1.2 and CC arms will be allowed to use their assigned product from the time of check-in until around 11:00 PM. On the

Confidentiality Statement

Data and information contained in this document are considered to constitute trade secrets and confidential commercial information, and the legal protections provided to such trade secrets and confidential information are hereby claimed under the provisions of applicable law. No part of this document may be publicly disclosed without the written consent of Philip Morris Products S.A.

second day of Visit 2 and Visit 3 product use will be allowed from 06:30 AM onwards. The exposure period to the assigned IP will end at 11:00 PM on the first day of Visit 4. On the second day of Visit 4 (Day 91), subjects who wish to smoke CC or use other nicotine/tobacco-containing products will be allowed to do so, but only after the end of 24-hour urine collection and after spirometry and sampling for CYP2A6 activity have been performed.

During the ambulatory visits (Visit 2, Visit 3, Visit 4) the use of CHTP 1.2 will be strictly forbidden for subjects in the CC arm.

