6.7.2.2 Ambulatory Period

The above dietary restrictions are not applicable for the ambulatory period.

One day prior to Visit 2, Visit 3, Visit 4, and during the visit on site, subjects will be asked by the site staff to refrain from consuming grapefruit or grapefruit-containing products, or quinine-containing drinks (e.g., tonic water). Alcohol, broccoli, brussels sprouts, cauliflower, chargrilled meat, xanthine-containing foods and beverages (e.g., coffee, tea, chocolate, cocoa, mate, guarana) will not be allowed on site during Visit 4.

A fasting state has to be observed for at least 10 hours prior to blood drawing for:

- Safety laboratory at Visit 2, Visit 3 and Visit 4
- Clinical risk endpoints' assessments in serum/plasma/blood at Visit 2, Visit 3 and Visit 4
- Serum/plasma bio-banking samples for BoExp, clinical risk endpoints and other circulating proteins, at Visit 4
- Blood bio-banking for transcriptomics, lipidomics and DNA methylation sequencing analyses at Visit 4

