During the visit		Collection of empty/partially used CHTP 1.2 packs for accountability	At any time of the day Partially used packs will be returned and/or new packs will be handed out to the subject for use until 11:00 PM at the latest.
End of day		Collection of empty/partially used CHTP 1.2 packs used during the day for final accountability	All packs must be returned to study staff at the end of Day 90.

Abbreviations: AE = Adverse event; CAF = Caffein; CC = Combustible cigarette(s); CHTP 1.2 = Carbon Heated Tobacco Product 1.2; CO = Carbon monoxide; COHb = Carboxyhemoglobin; CYP1A2 = Cytochrome P450 1A2; FTND = Fagerström Test for Nicotine Dependence; IP = Investigational product; MCEQ = Modified Cigarette Evaluation Questionnaire; QSU-brief = Questionnaire of Smoking Urges (brief version); SAE = Serious adverse event

Table 18 shows the assessments that will be performed on the second day of Visit 4 prior to Discharge from the ambulatory period.

Table 18 Time Schedule – The Second Day of Visit 4 (Day 91)

Time	Blood Sample	Procedures	Additional Information
Start of Procedure		Day 91	
		AE/SAE recording	At any time of the day
		Concomitant medications	At any time of the day
		End of 24-hour urine sample collection for Day 90 (the first day of Visit 4)	The urine is collected for 24 hours \pm 1 hour. The end of the 24-hour urine collection should be prior to smoking

Confidentiality Statement

Data and information contained in this document are considered to constitute trade secrets and confidential commercial information, and the legal protections provided to such trade secrets and confidential information are hereby claimed under the provisions of applicable law. No part of this document may be publicly disclosed without the written consent of Philip Morris Products S.A.

Time	Blood Sample	Procedures	Additional Information
Start of Procedure		Day 91	
			the first CC/using other nicotine/tobacco-containing products.
		Urine sample to be taken from the 24-hour urine of Day 90 (the first day of Visit 4)	Aliquots from 24-hour urine will be collected according to Table A2 . Bio-banking for biomarkers (if additional consent is obtained)

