Prior to 11:30 AM	√	Clinical laboratory parameters* (hematology, clinical chemistry) and cardiovascular clinical risk endpoints (hs-CRP, MPO, fibrinogen, homocysteine, , LDL, HDL, HbA1c, sICAM-1, Apo A1, Apo B, 8-epi-PGF2α, PGF2α [‡]), clinical risk endpoints of oxidative stress (4-HNE, TAC)	After at least 10 hours of fasting. * Blood glucose, TG, TC, WBC, platelet count from safety will be also evaluated as clinical risk endpoints [‡] As of 01 June 2016 blood samples for 8-epi-PGF2α/PGF2α will no longer be collected.
Prior to 11:30 AM	√	Bio-banking for BoExp, clinical risk endpoints and other circulating proteins, and transcriptomics, lipidomics and DNA methylation sequencing	If additional consent is signed After at least 10 hours of fasting
Prior to 11:30 AM		Spirometry pre- and post-bronchodilator (recording of FEV ₁ , FVC, FEV ₁ /FVC)	Has to be done prior to use of CC or other nicotine/tobacco-containing products At rest in sitting position for at least 15 minutes prior to pulmonary function testing In sitting position All post-bronchodilator spirometry testing will be performed 15-30 minutes

Confidentiality Statement

Data and information contained in this document are considered to constitute trade secrets and confidential commercial information, and the legal protections provided to such trade secrets and confidential information are hereby claimed under the provisions of applicable law. No part of this document may be publicly disclosed without the written consent of Philip Morris Products S.A.

Time	Blood Sample	Procedures	Additional Information
Start of Procedure		Day 91	
Prior to 11:30 AM	√	CYP2A6 activity in plasma	post administration of salbutamol Has to be done prior to use of CC or other nicotine/tobacco-containing products
Prior to 11:30 AM		Assessment of cough (VAS)	Irrespective of the time of CC or other nicotine/tobacco-containing products use
Before Discharge		ITUQ Questionnaire	
Before Discharge		Vital signs (blood pressure, pulse rate, respiratory rate)	At least 5 minutes in supine position, at least 15 minutes after having stopped using CC or other nicotine/tobacco-containing products
Before Discharge		Physical examination, body weight, and calculated BMI	
Before Discharge		Waist circumference	
Before Discharge		Safety urine analysis	
Before Discharge		Urine pregnancy test (females only)	
Before Discharge		ECG	At least 10 minutes in supine position prior to recording

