On the second day of Day 90 Visit, subjects who wish to smoke CC or use other nicotine/tobacco-containing products will be allowed to do so, but only after the end of 24-hour urine collection and after spirometry and sampling for CYP2A6 activity have been performed.

During the visits, the dispense and use of CHTP 1.2 will be strictly forbidden for subjects in the CC arm.

Subjects will not be discontinued from the study for the use of nicotine/tobacco containing products other than the assigned product/regimen during the ambulatory period. Subjects will record in a product use diary any use of CC (menthol or non-menthol), nicotine replacement therapy (NRT), or other nicotine/tobacco-containing products on a daily basis.

During the confinement and ambulatory settings:

- Any subject, who wants to attempt to quit using any tobacco products during the study (e.g., CHTP 1.2 and CC) will be encouraged to do so and will be referred to appropriate medical services. This will not affect subject's financial compensation, and the subject will remain in the study.
- The Safety Follow-up Period (from Discharge at Day 90 Visit until the End of the Safety Follow-up Period):

After Discharge at Day 90 Visit or the date of early termination, subject will enter a 28-day Safety Follow-up Period during which there will be recording of spontaneously reported new AEs/SAEs and the active follow-up of ongoing AEs/SAEs by the study site. In general, all AEs will be followed-up until resolved, stabilized (i.e., no worsening of the event), or a plausible explanation for the event has been found until the end of the study. At the end of the Safety Follow-up Period, all ongoing AEs will be documented as "ongoing" and will not be followed-up by

the Investigator. At the discretion of the Investigator, the subject will be referred to his General Practitioner for follow-up on ongoing AEs.

AEs with onset after the end of the Safety Follow-Up Period and considered related to the IP might be reported to the Sponsor. Such AEs may not be part of the study report.

SAEs spontaneously reported to the PI after the end of the Safety Follow-Up Period and considered related to the IP must also be reported to the Sponsor. Such SAEs may not be part of the study.

The individual end of study (EOS) date for a subject is defined as either the Discharge at Day 90 Visit or the date of early termination followed by the 28-day Safety Follow-up Period.

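### On Day 91 nothing places the fasting blood draw before permitted tobacco use, so CHTP 1.2 subjects could smoke cigarettes before their Visit 4 risk-endpoint bloods are taken

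*Protocol*

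**What the plan says.** The Day 91 permission is given in the Protocol Synopsis and sections 4.1, 6.3.4, 6.6.1 and 6.7.1.2. Tobacco or nicotine use may resume, "but only after the end of 24-hour urine collection and after spirometry and sampling for CYP2A6 activity have been performed". SAP 6.1 repeats the same three conditions: "urine collection and after spirometry and sampling for CYP2A6 activity have been performed".

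By then CHTP 1.2 is no longer available. Protocol 6.7.1.2 states: "The exposure period to the assigned IP will end at 11:00 PM on the first day of Visit 4". Section 6.6.2 adds: "All packs must be returned to study staff at the end of the first day of Visit 4".

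Table 18 (Protocol 9.3) schedules Day 91. Spirometry and CYP2A6 each carry the note "Has to be done prior to use of CC or other nicotine/tobacco-containing products". There are two fasting blood rows. One covers the safety laboratory, cardiovascular risk markers and oxidative-stress markers; the other covers bio-banking. Both carry only an 11:30 AM limit and a fast of at least 10 hours. The fasting rule itself sits under dietary restrictions (6.7.2.2), where it covers clinical risk endpoint "assessments in serum/plasma/blood at Visit 2, Visit 3 and Visit 4" and does not mention smoking.

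SAP Table 14 shows the same contrast. CYP2A6 must precede product use; the risk-endpoint bloods have a clock limit only.

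**The concern.** The Day 91 bloods supply the Visit 4 values for most of secondary objective 6 and for TAC under objective 7. In the ambulatory period, the Day 90 Visit is the only point at which SAP 12.5.2.6 and 12.5.2.7 compare these markers formally between arms. HbA1c, Apo A1 and Apo B have no other post-baseline sample.

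A subject and site that follow the plan exactly could finish urine collection, spirometry and the CYP2A6 sample, allow a cigarette, and then draw the fasting blood. In the CC arm that cigarette is the same product as in the preceding 90 days. In the CHTP 1.2 arm it is comparator exposure shortly before an endpoint sample. For any marker that responds to recent smoking, this would make the arms look more alike. Because the use is permitted, it would not be a protocol deviation.

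**Working it through.** The plan states no figure on this point, so there is none to reproduce. The check compares the rules and then does clock arithmetic.

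**1. Conditions on each Day 91 assessment**

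| Assessment | In the smoking hold? | Tobacco condition in Table 18 | SAP Table 14 |
|---|---|---|---|
| 24-h urine | Yes | Ends before smoking | Start time and duration |
| Spirometry | Yes | Yes | Before product use |
| CYP2A6 blood | Yes | Yes | Before product use |
| Fasting risk-endpoint and safety blood | No | None | Before 11:30 AM only |
| Bio-banking blood | No | None | Not listed |

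No section orders the fasting draw before spirometry or CYP2A6. Table 18 also foresees tobacco use before some Day 91 assessments: its vital-signs row asks only for a 15-minute gap after cigarettes or other products.

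**2. The time available**

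Inputs from Table 17: urine collection starts at 09:00 ± 30 min on Day 90 and lasts 24 ± 1 h. Input from Table 18: blood is due before 11:30 on Day 91.

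- Earliest end: 08:30 + 23 h = 07:30. Gap: 11:30 − 07:30 = 4.0 h.
- Nominal end: 09:00 + 24 h = 09:00. Gap: 2.5 h.
- Latest end: 09:30 + 25 h = 10:30. Gap: 1.0 h.

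These gaps are upper bounds, because spirometry (with a 15 to 30 minute wait after the bronchodilator) and CYP2A6 must also be finished before tobacco use.

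**3. Whether other rules would catch it**

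These endpoints are analysed in the per-protocol populations. SAP Table 12 makes a CHTP-arm subject non-compliant with more than 2 CC in one day or an average above 0.5 CC per day from Day 1. One or two cigarettes on Day 91 do not break the first limit. They add at most 2/90 ≈ 0.02 to the average. SAP 11.4 gives no example of invalid data for tobacco use before these bloods.

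**4. Which endpoints are exposed**

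- Not exposed: the primary endpoints. COHb, MHBMA, 3-HPMA and S-PMA are Day 5 endpoints, and Visit 4 total NNAL is in the 24-h urine.
- Not exposed: 11-DTX-B2, 8-epi-PGF2α and 8-OHdG in urine, which the hold covers.
- Not exposed: Visit 4 COHb, exhaled CO, plasma nicotine and cotinine, and CYP1A2, all taken on Day 90.
- Not relevant to a formal comparison: 4-HNE (not assayed) and the plasma 8-epi-PGF2α/PGF2α ratio (listed only).
- Exposed: hs-CRP, MPO, fibrinogen, homocysteine, LDL, HDL, HbA1c, sICAM-1, Apo A1, Apo B, glucose, TG, TC, WBC, platelets and TAC, plus the remaining safety laboratory and bio-banking blood.

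**The case against.** The case for leaving the text alone has substance.

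- CYP2A6 is itself a morning blood sample due before 11:30 and before tobacco use, and subjects are on site and fasting. One venipuncture for everything is the natural workflow. This stands as a reason why the problem may never have arisen, but no section requires it.
- The fasting draws on Day -1 and Days 31 and 61 carry no tobacco condition either, so the plan does not generally treat these bloods as needing abstinence. That is true. Day 91 differs in the product: on the other days it is the usual cigarette before randomization or the assigned product after it, while on Day 91 CHTP 1.2 is withdrawn and cigarettes are expressly allowed.
- The per-protocol limits leave a CHTP 1.2 group that smokes few cigarettes. Section 4.2 describes the smoking-sensitive markers it names (HDL, sICAM-1, WBC and 8-epi-PGF2α) as shifting over one to three months of cessation. Both facts argue for a small effect, and the documents show no analysed blood marker that responds within hours.
- The endpoints are secondary and outside the multiplicity procedure, and bias toward no difference does not manufacture a benefit. This stands and limits the importance of the point.

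A reader might infer from the missing Day 91 diary mark in Table A1 that nothing records who smoked. The documents do not support that: Protocol 6.6.4 and 7.7.1 and Table A1 footnote j run the diary to discharge at Visit 4, which is on Day 91. What is missing is a required clock time of use relative to the draw.

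**Conclusion.** The gap in the written rules is real and appears in both documents. Following them exactly permits comparator cigarettes in the CHTP 1.2 arm before the Visit 4 fasting bloods. The documents do not show that it happened.

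The direction is toward no difference, on the assumption that a cigarette moves a marker toward the level seen in continuing smokers. A reader might want to attach a percentage loss to the contrast. That would need the share of CHTP-arm subjects who smoke before the draw and the share of the arm difference that one or two cigarettes restore. The documents give neither, so no figure is offered. A reader might also infer that the oxidative-stress objective as a whole is compromised; TAC is the only formally analysed oxidative-stress marker exposed.

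This is a modest point about secondary endpoints. It merits action because the risk falls mainly on one arm and the remedy costs almost nothing.

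**What to change.** 1. Reconcile the Day 91 hold with Table 18 and SAP Table 14. Both fasting blood rows in Table 18 should carry the sampling-order condition already given to CYP2A6 and spirometry, for example by drawing them with the CYP2A6 sample. Repeat the addition wherever the hold appears: Synopsis, 4.1, 6.3.4, 6.6.1 and 6.7.1.2 of the Protocol, and 6.1 of the SAP.

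2. For subjects already sampled, use the data review before database lock (SAP 11.1 and 11.4). Check Day 91 draw times against recorded product use, and report by arm how many draws followed recorded use and how many cannot be ordered. Draw times should exist, since SAP Table 13 counts a missing assessment time as a deviation.

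3. Where use before the draw is recorded, report a sensitivity analysis of the Day 90 Visit comparison with the same rule in both arms. Discarding such samples in the CHTP 1.2 arm alone would be an arm-specific exclusion after randomization and could itself bias the contrast. Even a common rule selects on behaviour after randomization, so it should support the planned analysis and not replace it.

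4. In the same edit, reconcile the timing of Visit 4 blood pressure: Table 18 and the Table A1 grid place vital signs on Day 91, while Table A1 footnote a places the blood-pressure risk marker on the first day of the visit.

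Cost: wording changes, one check at a review already planned, and a slightly longer wait before first product use on Day 91.
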